**Table 3: Study Visit Timeline for Immediate Intervention Group\***

Format and timing of visits	Key activities
Baseline Data Collection	Sweatpatch application Heartrate Variability Measurement Survey
Sweatpatch Pickup	72 hours post-application, remove sweatpatch and deliver for storage and analysis
Randomization	Mail randomization results
Home Visit Week 1	Assessment Set goals and discuss priorities Remove sweatpatch and deliver for storage and analysis (if not already performed)
Home Visit Week 3	Purpose in Life activity Instrumental Support activity: Benefits Check Up Assess goal attainment and revisit strategies
Phone Check-in Week 4	Review/edit purpose statement Assess goal attainment and strategies to achieve goal
Home Visit Week 6	Social Support Activity Assess goal attainment and strategies to achieve goal Follow-up re: instrumental support
Phone Check-in Week 8	Review/edit purpose statement Assess goal attainment and strategies to achieve goal
Home Visit Week 10	Assess goal attainment and strategies to achieve goal Follow-up re: instrumental and social support
Phone Check-in Week 12	Review/edit purpose statement Assess goal attainment and strategies to achieve goal
Home Visit Week 14	Review of progress, goals and purpose Discuss how caregiver will involve social support in next goals
Data Collection Visit Week 16	Sweatpatch application Heartrate Variability Measurement Survey
Sweatpatch Pickup	72 hours post application
Data Collection Visit Week 32	Sweatpatch application Heartrate Variability Measurement Survey
Sweatpatch Pickup	72 hours post application

\* Waitlist control group will begin intervention at week 16.

### Research Variables and Measurement

We chose measures (Table 1) based on previous RCT experience as well as those that met the following criteria: 1) possess known reliability and validity with ethnically diverse samples; 2) are sensitive to change from an intervention; 3) have clinical relevance to QOL; 4) Common Data Elements to connect this work with the broader literature, other pilots and other P30 Center work and 5) represent objective as well as subjective indicators of the domains we seek to impact. Finally, we sought to achieve a balance between psychometric quality and practical considerations such as respondent burden. All instruments with the exception of demographics will be measured at baseline and 16 weeks post-intervention.

**Table 4: Constructs, Instruments and Reliability**

Theoretical Construct	Instruments and variables	Number of Items	Cronbach's alpha
Caregiver demographics and characteristics	Demographics Characteristics: Caregiving physical and supportive tasks description, employment Physical Activity Readiness Assessment	23	-
Fatigue	PROMIS-Fatigue Short form	7	0.9 
Caregiver Burden	Oberst Caregiver Burden Scale 2 domains: time caregiving and task difficulty	15	0.90 
	Modified Caregiver Strain Index	13	0.86 
	ENRICHED Social Support	7	0.89 
Social Support	Family Functioning – Family Assessment Device Questionnaire: Global Family Functioning Scale (only)	12	0.9 
	Sweatpatch (IL6, IL10)	-	-
	Coping Self-Efficacy Scale	13	0.91 
Resilience	Heart Rate Variability	-	-
	Brief Resilience Scale	8	0.91 
Quality of Life	36-Item Short Form Health Survey (SF-36) 2 scales: Affective well-being and Physical health	36	0.85 
Depression	PHQ-8	8	0.82 
Care Recipient Palliative Care Utilization	Palliative care referral or encounter in electronic medical record within 6 months after caregiver completion of intervention	-	-
Care Recipient Hospitalization	Hospitalization (admission) encounter in electronic medical record within 6 months after caregiver completion of the intervention	-	-
Care Recipient Mortality	Documented as deceased in electronic medical record within 6 months after caregiver completion of the intervention	-	-
Care Recipient Hospice Enrollment	Enrollment in hospice in the electronic medical record within 6 months after caregiver completion of the intervention	-	-

**Data collection and management:**Questionnaire Data:

Trained research assistants will verbally elicit questionnaire data from participants in person or in virtual meetings. Virtual meetings include either telephone conversations or video calls via DoxyMe or Zoom. DoxyMe is a HIPAA compliant virtual meeting software used for telehealth purposes. We have created a HIPAA compliant Zoom account for video calls as well. Research assistants will directly enter data into the RedCap data entry and management system.

Due to COVID-19 research restrictions we will not collect sweat patch or HRV data until approved by the School of Nursing research restart committee.

Sweat patch:

Interleukin 6 & 10 will be collected via a non-occlusive adhesive patch which remains in place on the caregivers' skin for 72 hours. The sweat patch will be placed on the participant's skin at their baseline data collection visit. The participant will be instructed to leave the sweat patch in place for 72 hours. A study team member will then return to the participant's home to remove the sweat patch. The sweat patches will be prepared and delivered to the Johns Hopkins School of Nursing for temporary storage. Then the patches will be analyzed at the Johns Hopkins School of Nursing according to the Gill Lab Sweat Patch Extraction protocol and analyzed using a 3-step digital immunoassay, running all samples in duplicate. Due to COVID-19 research restrictions, sweat patches will not be utilized until the Johns Hopkins University IRB phase 2A to allow study team members to go to participants homes.

#### HRV:

An electrocardiogram approximately 5 minutes in length will be captured using the commercially available KardiaMobile ECG device (AliveCor, San Francisco, CA, USA). Participants will place their forefingers on the touch pad while seated and resting for the reading. Data will be captured using Kubios HRV software, a software tool for heart rate variability analysis (Kubios, Inc. Kuopio, Eastern Finland). The device will automatically save the rhythm strip on the iPod app and study personnel will download the rhythm strip after the home visit when it is performed. The file will be sent to the University of Oklahoma Heart Rate Variability Laboratory where it will be analyzed for measures of heart rate variability and counts of abnormal beats (if any). These files will have no identifying data other than time and date of measurement. If any suspected abnormality is seen on the analysis, the PI will be notified of any abnormalities that could impact health, and the subject would be notified and informed to contact their physician. Due to COVID-19 research restrictions, sweat patches will not be utilized until the Johns Hopkins University IRB phase 2A to allow study team members to go to participants homes.

#### Physical Readiness Assessment

During the course of this intervention, the participant will be developing personal goals with the guidance of the nurse interventionist. If a physical activity goal is identified, the nurse interventionist will administer the Physical Readiness Assessment tool. The results of the physical activity readiness assessment will be evaluated by the study nurse practitioner - [name], CRNP, FNP-BC - to determine the safety of the participant's physical activity goal. Due to COVID-19 research restrictions, the physical readiness assessment will not be performed, and physical activity goals will not be pursued for participants who have virtual data collection and intervention interactions.

#### Care Recipient Data:

Six months after the caregiver completes the intervention, trained research assistants will search the electronic medical record of the caregiver's care recipient related to palliative care utilization (referral), hospice enrollment, hospitalization (admission), and death. Research assistants will directly enter data into the RedCap data entry and management system.

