### 2. Objectives

Aim 1: Test the feasibility and gauge an initial effect size of the intervention to improve QOL (primary outcome), fatigue and caregiver burden (secondary outcomes) among family caregivers from baseline to 16 weeks.

Aim 2: Test whether fatigue and caregiver burden are associated with a physiological measure of resilience, inflammatory cytokines (IL-6 and IL-10) detected in sweat patches and a self-reported measure of resilience, controlling for covariates.

Aim 3: Evaluate changes in heart rate variability (HRV), an indicator of physiologic stress, pre- and post-intervention.

Aim 4: Describe care recipient 6-month palliative care utilization, all-cause hospitalization, and mortality, comparing intervention and control.

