## 4. Study Procedures

**Figure 2: Flowchart of Study Design**

control groups are used to first provide an untreated comparison and second to allow wait-listed participants an opportunity to receive the intervention at a later date. This is especially appropriate given that very few services are currently offered to HF caregivers. To account for estimated 20% attrition we will recruit 53 participants.

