### b. Secondary outcome variables.

Generalized estimating equations (GEE) will be used to examine the difference between intervention and waitlist groups in change from baseline to 16 and to 32 weeks for fatigue and caregiver burden (secondary outcomes) using a similar approach (as described for primary outcome). We will use a similar approach to analyze cytokines and HRV. Given previous research in adults with chronic disease, we assume that the cytokine data will require log transformation to approach normality.

We compare differences in care recipient palliative care utilization, hospice enrollment, hospital admission, and mortality 6 months after caregiver completion of the intervention between intervention and control groups. We will use chi-square test to determine differences in rates of these outcomes and t-tests to compare average time to event between groups.

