**Recruitment, Adverse Events (AE) and Alert Reports:** Reports presented to the DSMB will include data on enrollment (study accrual by month; comparison of expected to actual enrollment; number of individuals screened, number eligible and number ineligible, number randomized by gender), AEs, and alerts. Also, the DSMB will receive reports of the number of study participants who discontinue from the treatment group and/or the study and reasons for discontinuation. We propose that reports be provided to the DSMB twice yearly. However, the DSMB will decide upon the schedule of reports at their first organizational meeting. Also, the DSMB may request reports as needed as well as the unmasking of the data should they deem this necessary. If unmasked efficacy data is required, the biostatistician for this study ([name]) will serve as a liaison between the PI, database and the DSMB in order to assure that the PI and investigative team remains masked. For the first meeting of the DSMB, members will receive and review the following materials: a) Grant proposal, relevant appendices, reviewers' comments; b) Standard Quality control procedures (see Facilities/Resources); c) IRB approved consent forms; d) Baseline and follow-up batteries; e) Shell of data base for management of interview schedules and enrollment information; f) Subject tracking forms; g) Alerts and Adverse event procedures and forms; h) Intervention treatment documentation forms; i) Shell for reporting recruitment and enrollment; j) Data shells for reporting tracking information and baseline characteristics; k) Decision rules for intervention termination (e.g., death, extended hospitalization, relocation);

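### Aim 4 counts care-recipient outcomes only from the caregiver's completion of the intervention, so caregivers who stop early have no index date and deaths before completion fall outside the window

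*Combined protocol and SAP*

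**What the plan says.** Section 4, Care Recipient Data, sets the timing of the chart review: "Six months after the caregiver completes the intervention, trained research assistants will search the electronic medical record". Table 4 defines all four care-recipient outcomes from the same point. Mortality is "Documented as deceased in electronic medical record within 6 months after caregiver completion of the intervention", and admission is "Hospitalization (admission) encounter in electronic medical record within 6 months after caregiver completion of the intervention". Section 7.b then compares "mortality 6 months after caregiver completion of the intervention between intervention and control groups" and adds: "We will use chi-square test to determine differences in rates of these outcomes and t-tests to compare average time to event between groups".

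Aim 4 in Section 2 gives a six-month period without a start: "Describe care recipient 6-month palliative care utilization, all-cause hospitalization, and mortality, comparing intervention and control".

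No section offers another index date, defines completion, or orders a chart search when a caregiver stops early. The entry in Section 4 on participation that ends prematurely is marked not applicable. Section 7.c separates non-compliance from loss to follow-up but sets no rule for these outcomes.

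Table 3 puts the last intervention visit at week 14 for the immediate arm, and its footnote starts the waitlist arm at week 16.

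**The concern.** Completion is a post-randomisation event. A care recipient's decline or death can plausibly end the caregiving role and the sessions with it, so the outcome can influence who is counted. There are two routes by which a patient or an event is lost:

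- The caregiver stops early. There is no completion date, so the written rule triggers no search and the patient drops out of the comparison.
- The caregiver completes after the patient has died. The death precedes the Table 4 window. The documents do not say whether that patient leaves the denominator or stays in it as a non-event.

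The excluded period is also about twice as long in the waitlist arm. The rates compared are therefore not rates in the groups as randomised. Care recipients must have been hospitalised in the previous 6 months (Section 5), so early events are plausible.

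**Working it through.** The plan gives no event rate, event count or power for Aim 4, so there is no figure of its own to reproduce. What follows is an illustration.

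**Inputs**
- Arm size: 20 and 20 (Section 4, Overview of Study Design).
- Completion: week 14 in the immediate arm (Table 3); 16 + 14 = week 30 in the waitlist arm, assuming the same schedule.
- Window: 26 weeks after completion, so weeks 14–40 and 30–56.
- Mortality: 53% at 5 years after heart failure hospitalisation (Section 3). The constant hazard is an assumption: λ = −ln(1 − 0.53)/5 = 0.151 per year. Two and three times λ are shown because recent hospitalisation may raise early risk.

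**Step 1. Deaths before and inside the window**

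Before: 1 − exp(−λt/52). To window end: 1 − exp(−λ(t + 26)/52). Inside: the difference.

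At λ = 0.151:
- Immediate, t = 14: before 0.0398, to window end 0.1097, inside 0.0698.
- Waitlist, t = 30: before 0.0834, to window end 0.1501, inside 0.0667.

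| Hazard | Before window, per 20 (imm. / wait.) | Inside window, per 20 (imm. / wait.) | Share of deaths uncounted (imm. / wait.) |
|---|---|---|---|
| λ | 0.8 / 1.7 | 1.4 / 1.3 | 36% / 56% |
| 2λ | 1.6 / 3.2 | 2.6 / 2.4 | 38% / 58% |
| 3λ | 2.3 / 4.6 | 3.6 / 3.1 | 39% / 60% |

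The shares cover unequal spans (40 and 56 weeks from randomisation). They measure events not counted, not bias between arms.

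**Step 2. Does this alone create a difference when the intervention does nothing?**

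Among patients alive when the window opens, a constant hazard gives 1 − exp(−0.151 × 26/52) = 7.3% in both arms, so no difference.

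If early deaths stay in the denominator as non-events, the rates are 7.0% and 6.7%. The gap is 20 × (0.0698 − 0.0667) = 0.06 deaths per 20. At 2λ it is 20 × (0.1292 − 0.1177) = 0.23, and at 3λ it is 20 × (0.1794 − 0.1561) = 0.47.

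**Step 3. A hazard that falls with time**

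Assume 3λ = 0.453 per year for the first 26 weeks after randomisation, then λ, with no treatment effect.
- Immediate window, weeks 14–40: 12 weeks at 0.453 and 14 weeks at 0.151. Cumulative hazard = 0.453 × 12/52 + 0.151 × 14/52 = 0.145; risk among survivors = 1 − exp(−0.145) = 13.5%.
- Waitlist window, weeks 30–56: 26 weeks at 0.151. Cumulative hazard = 0.0755; risk = 7.3%.

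The immediate arm then looks worse only because its window opens earlier.

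**The case against.** The strongest reply is that the selection produces almost no spurious difference under the simplest model, and Step 2 confirms it. A reader might infer from 36% versus 56% that the comparison is biased whatever the truth. The documents do not support that: with a constant hazard and equal non-completion, the survivor risks are identical. Bias needs one of the further conditions in Step 3 or the verdict.

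Three other strong readings should also be resisted.

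- That non-completers' patients can never be counted. No passage excludes them, completion is undefined, and staff might search from a planned date. What stands is that the written rule gives no date from which to do so.
- That four of 20 per arm would be lost. The protocol says "To account for estimated 20% attrition we will recruit 53 participants", and 20 per arm matches the planned trial of 40, so taking a further 20% off may count attrition twice. Attrition is also not the same as non-completion, and Section 7.c says the two will be distinguished. The number of non-completers is not given.
- That the protocol itself makes the patient's death a reason to end the intervention. Section 8 lists "Decision rules for intervention termination (e.g., death, extended hospitalization, relocation" among materials for the data safety and monitoring board. It does not say whose death, and the surrounding text concerns study participants, who are caregivers. The point does not rely on it.

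It is also fair that Aim 4 is descriptive, in a pilot that expects low power. But Section 7.b does plan between-arm tests, and with about one counted death per arm each uncounted event matters.

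**Conclusion.** The point holds as a defect in how Aim 4 is defined. The search, the outcome windows and the comparison all start at a post-randomisation event that occurs about 16 weeks later in one arm than in the other. Following the rule as written loses patients and early events from the randomised comparison.

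The loss in Step 1 rests on a constant hazard from a five-year figure, the same visit schedule in both arms and 20 per arm.

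Whether the loss also biases the comparison is conditional. It does so with no treatment effect if risk falls with time since hospitalisation, if frailer patients die first, or if non-completion differs by arm. The 13.5% versus 7.3% example shows that the first of these can matter; it is not a forecast.

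The correction is worth making, but it concerns a secondary, descriptive aim and leaves the primary quality-of-life analysis unaffected.

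**What to change.** Amend Care Recipient Data in Section 4, the four care-recipient rows of Table 4, and Section 7.b as follows:

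- Search the record of the care recipient of every randomised caregiver, whether or not sessions were completed.
- Count deaths, hospice enrolments, admissions and palliative care referrals or encounters from randomisation, over the same fixed length of time in both arms, and state that length.
- Use the care recipients of all randomised caregivers as the denominator.
- Keep the completion-anchored window only as a supplementary description.

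Moving the start to each arm's scheduled last-session week would supply a date for non-completers. It would still leave earlier deaths outside the compared rate and keep the 14 versus 30 week difference, so randomisation is the better anchor. With a common start and length, any hazard shared by the arms gives equal expected risks when there is no effect. For illustration, 56 weeks would reach the end of both present windows, with 20 × 0.1501 = 3.0 expected deaths per arm at λ.

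The cost is wording plus a few more chart searches, with no new participants or visits. The price in interpretation is that the window covers the intervention period as well as the time after it. Beyond week 16 the contrast is between immediate and delayed intervention, and the report should say so.

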#### Data Management:

Data from screening, intervention sessions, and final data collection will be entered onto forms that the data manager will check for completeness and appropriateness. The data manager will send reports of missing or inappropriate entries to the PI every week for clarification and resolution. As a phase 1 pilot study, a Data Safety and Monitoring Board is not required, however, as part of the P30 PROMOTE Center, a Data Safety and Monitoring Board has been established. Details are provided in the human subjects section.

Fidelity: The fidelity plan is based on the NIH Behavior Change consortium developed by national leaders. We will enhance fidelity through design elements (intervention is distinct and based on theory), training (using an intervention manual), delivery (reminder calls the night before intervention sessions, and measure fidelity through records of home sessions (by date and duration), checklists completed by study team

members and direct observations and discussions concerning intervention engagement to evaluate receipt, and enactment. Ten percent of sessions will be audio taped which will be reviewed by the research coordinator using a priori monitoring checklists developed for this pilot trial. All data collection and intervention interactions will be recorded. Evaluation will include periodic assessments of data quality, participant recruitment, accrual, and retention. Feedback will be provided to each interventionist who will provide case presentations in supervisory sessions. Bi-weekly meetings of the nurse interventionist with the Research Coordinator, the PI, and [name] will assure on-going fidelity to the intervention.

**Study duration and number of study visits required of research participants:** Participation in the study will consist of initial study consent, baseline, 16 and 32-week data collection and 5 study interactions for the intervention. Based on participant preference, the nurse interventionist may also arrange phone calls between visits to assess progress towards goals.

**Blinding, including justification for blinding:**

Research staff performing outcome assessments will be masked to assignment. Prior to follow-up assessment, staff will use standardized language to instruct participants not to discuss their treatment allocation with staff.

Justification of why participants will not receive routine care or will have current therapy stopped: n/a

**Justification for inclusion of a placebo or non-treatment group:** Both groups will receive the intervention. We are using a waitlist design to have a comparison to usual care.

Definition of treatment failure or participant removal criteria: n/a

Description of what happens to participants receiving therapy when study ends or if a participant's participation in the study ends prematurely: n/a

## 5. Inclusion/Exclusion Criteria

Screening:

- 1) Six-Item Screener; Callahan CM et al., 2003

To be eligible for inclusion caregivers must:

- 1) 18 years or older and
- 2) English speaking
- 3) Live with the heart failure patient or visit the patient at least 3 days per week to provide care or support.
- 4) Provide support to the patient for at least 1 Instrumental Activity of Daily Living
- 5) Care for a heart failure patient hospitalized in the last 6 months
- 6) Live within a 1 hour driving radius of the Johns Hopkins Hospital

Exclusion Criteria:

- 1) Caregivers with cognitive impairment using the six-item screener will be excluded. Severe Cognitive Impairment would make active participation in interviews and survey completion very difficult.
- 2) Non-english speakers will be excluded. Non-english speakers may have unknown needs that cannot be addressed with this intervention.

- 3) Caregivers with terminal diagnosis will be excluded as goal-setting at end of life may be different than without a terminal diagnosis.

